TITLE PAGE

**Role of Linagliptin in improving renal failure by improving
CD34+ stem cell number, function and gene expression in renal
function impaired type 2 diabetes patients**

[name], MRCP (UK), PhD, FACP, FACE

George Washington University Medical Faculty Associates

[name]

[name]

Phone - [contact]

Protocol Version/Date: Version 6.9 / June 2017

PROTOCOL SYNOPSIS

Protocol Title:	Role of Linagliptin in improving renal failure by improving CD34+ stem cell number, function and gene expression in renal function impaired type 2 diabetes patients
Site Numbers & Names:	GWU Medical Faculty Associates
Research Hypothesis:	Both type 2 diabetes and CKD are associated with poor stem cell number and function. Poor viability and function of EPCs in CKD and diabetes affects the repair and regeneration of the endothelium and renal tubules. We hypothesize that use of Linagliptin (along with Insulin, metformin, or both) may help reduce cardiovascular risk by improving EPC survival and function above and beyond adequate glucose metabolism control.
Study Schema: Drugs / Doses / Length of Treatment)	We propose a 2-arm randomized, parallel group, longitudinal study of 12-week intervention duration. The 12-week time interval has been previously shown adequate to observe changes in biochemistry, EPCs and, importantly, pulse wave velocity (PWV) changes. Patients will be randomized to 2 groups: Control, (n=20), Insulin/Metformin + Lifestyle + Placebo. Treatment, (n=20) Insulin/Metformin + Lifestyle + Linagliptin 5mg.


Study Objectives:
 
 • Primary: • Secondary: 	
The primary objective is to ascertain if addition of Linagliptin improves CD34+ cell function and gene expression in early type 2 diabetes patients with CKD stage 1-3, which will be correlated to improvement in 24hr urinary protein estimation and creatinine clearance (obtained via micro-albumin/creatinine ratio from a spot urine sample).
 
The secondary objective is to correlate the cellular outcome measures with other measures of endothelial function such as:
 
 1. Arterial stiffness measures with pulse wave analysis and pulse wave velocity measurements 2. Serum biochemistry looking at surrogates of endothelial health, endothelial inflammation, appetite controlling hormone levels and fasting glucose, insulin and lipid profile. 3. Resting Metabolic Rate measurement 
Study Outcome Measures
 
Primary:
 
To investigate the effect of Linagliptin on Endothelial function in patients inadequately controlled (HbA1C ≥ 6.5 % to ≤ 10%) while being treated with stable Insulin, Metformin, or both.
 
 • Cellular markers. We will study pre and post Linagliptin treatment changes in number, function and gene expression of patients' peripheral blood-derived CD34+ cells. • 24hr urinary protein estimation and creatinine clearance. 
Secondary:
 
 • To investigate the effect of Linagliptin treatment on serum endothelial inflammatory markers including high sensitivity C-reactive protein (hs-CRP), IL-6, TNF-alpha, and fasting lipid profile including ApoA1 and ApoB. 
Glycemic control will be evaluated by measuring fasting blood glucose, insulin, and HbA1c levels and assessing insulin resistance using HOMA-IR
 
 • Adiposity, measured using the Tanita Body Composition Analyzer scale, measured as percentage body fat. • Estimation of Creatinine clearance and Proteinuria estimation. • Vessel health will be assessed by systolic and diastolic blood pressure and Arterial stiffness assessed using vascular flow and wave measurement equipment, SphygmoCor CP system from ATCOR. • The sphygmocor system also allows us to estimate central and aortic blood pressure. • Resting Metabolic Rate (RMR, similar to Resting Energy expenditure measurement) at baseline, midway point (week 6) and post therapy.
--	---

Study Design:	Prospective, double-masked, randomized placebo-controlled trial
Accrual Goal: (Total number of subjects)	N=40
Accrual Rate: (Number of subjects expected per month)	Recruit 40 patients in approximately 36 months.
Estimated: FPFV: LPFV: Follow Up: (dd-mm-yy)	FPFV: 09-15-2015. LPFV: 09-15-2018
Co-relative Studies: (PK/PD, etc.)	N/A
Inclusion Criteria:	
 1. Adults aged 40-70 years. 2. Diagnosis of type 2 diabetes within the previous 15 years using criteria of the American Diabetes Association 3. Currently treated with a stable dose of Insulin, Metformin (1-2 grams/day), or a stable combination of the two as therapy. 4. HbA1C between 6.5 to 10% (both inclusive) 5. BMI 25 to 39.9 kg/m² (both inclusive) 6. CKD stages 1-3

Exclusion Criteria:
	
Patients with:
 
 1. Implanted devices (e.g., pacemakers) that may interact with Tanita scale 2. Previous coronary or cerebrovascular event within 6 months of screening or active or clinically significant coronary and/or peripheral vascular disease 3. Low hematocrit (<28 UNITS). 4. Pre-existing liver disease and/or ALT and AST >2.5X's UNL 5. CKD stage 4 and 6. History of pancreatitis, or cancer (except basal cell carcinoma and cancer that is cured or not active or being treated in the past five years) 7. Statin use started or dose change in the last 3 months 8. Use of oral anti-diabetic medication other than Metformin, or Insulin. 9. Use of consistent long-term steroid medication in the last 3 months (oral, inhaled, injected). 10. Systolic BP> 140 mmHg and Diastolic BP> 90 mmHg 11. Active wounds or recent surgery within 3 months. 12. Inflammatory disease, or chronic current use of anti-inflammatory drugs within the last 3 months 13. triglycerides >450 mg/dL 14. untreated hyper/hypothyroidism 15. Auto antibody confirmed type 1 diabetes 
Additionally, patients who are active smokers, patients who are pregnant, nursing women, and post-menopausal women who are on hormone replacement therapy will be excluded.
 
Patients on low dose oral contraceptives will be allowed to participate as these formulations contain lesser amount of estrogens.

-----------------------------------	---


Criteria for Evaluation: (Efficacy, safety, stopping rules, etc.)
	
Subjects will be screened at week -4, then evaluated for end points at weeks 0, 6 and 12. Follow up phone call will be done 30 days after last dose of study drug to assess for adverse effects.
 
Study participation will be stopped for adverse effects at the discretion of the study investigator. Subjects may stop study participation at any time and for any reason.

Statistics:
	
The total sample size is requested, after accounting for attrition over the 12-week period, is 20 subjects per group or 40 subjects total. Sample size estimates were based on the effects of exercise on CD34+/KDR+ cells as described in the literature. The effect of a single session, as well as extended training, on healthy subjects or those with existing cardiovascular conditions appears to increase the CD34+/KDR+ cells.
 
This is a pilot study as a result appropriate power calculation is not feasible. We however did conduct power analysis, which provided us with 73% power (see statistics section). A p-value of less than 0.05 will be considered statistically significant.

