1 INTRODUCTION

Type 2 diabetes is a national epidemic (1, 2) with significant macro and microvascular complications (3). Insulin resistance in pre-diabetes and overt diabetes are associated with endothelial dysfunction (4).

A few studies indicate that stem cells particularly EPCs can act as a suitable bio-marker (5-7, 9) for monitoring cardiovascular morbidity. In this proposal we suggest that EPCs or CD34 positive cells (defined as CD34/VEGFR2+ cells) can act as a suitable cellular biomarker for estimating and following endothelial dysfunction in early type 2 diabetes patients with CKD. EPCs have been shown to be dysfunctional in both CKD patients and type 2 DM patients. (5, 7, 31, 35)

Linagliptin (TRADJENTA) tablets are indicated as an adjunct to diet and exercise to improve glycemic control in adults with type 2 diabetes mellitus. No dose adjustment is recommended for patients with renal impairment. (29)

EPCs have been used as a regenerative tool in ischemic myocardium and diabetic wound healing (8, 10-13). Endothelial dysfunction with associated inflammation may be a consequence of excess intra-cellular super-oxide presence in a setting of diabetes which is a pro-oxidative stress condition ultimately leading to poor EPC function and senescence (14).

Though lifestyle modification has been proposed as a main stay for prevention and treatment of early type 2 diabetes, (2, 15-19) several new therapies for diabetes have been developed in recent years (2). Incretins and incretin mimetics appear to hold promise. Mechanism of positive effect of exercise and oral hypoglycemic agents can be very different. (44-50)

DPP-4 inhibitors have been shown to increase EPCs in patients with type 2 diabetes (20) reportedly via SDF-1 alpha up-regulation. Interestingly, up-regulation of SDF-1 alpha and vascular endothelial growth factor (VEGF), both chemotactic factors increase mobilization and recruitment of EPCs in the face of acute ischemic injury for repair and regeneration. (21-24).

Several studies have shown positive effect of incretins (Glucagon like peptide, GLP-1) and incretin receptor agonists (GLP-1 receptor agonists) on cardiovascular risk factors in type 2 diabetes patients (20, 25) and even in patients with chronic heart failure and left ventricular dysfunction who do not have diabetes (26, 27).

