DPP-4 Inhibitors may have cardio-protective effects of their own, as they increase bio-availability of endogenous GLP-1. They improve blood flow and nitric oxide production in

endothelium (28, 29). These are unique properties not demonstrated by other oral diabetes medications (29). The mechanism underlying these effects may be mediated by increased nitric oxide bioavailability but is not completely known. However these beneficial effects appear to be independent of glycemia reduction.

It is however unknown whether Linagliptin will have any positive effect on human EPC function where two prominent cardiovascular risk factors co-exist such as CKD and type 2 diabetes.

Therefore we plan to investigate if Linagliptin can alter function and gene expression of CD34+ cells in a setting of CKD and type 2 diabetes. We choose to look at non geriatric adult population with early type 2 diabetes (≤ 15 years of duration) at an early phase of renal impairment (stages 1-3).

We specifically choose to exclude known CVD disease patients and early type 2 DM patients with early CKD as this cohort may be still retain capability to reverse or halt persistent endothelial damage seen in type 2 diabetes and CKD (3,30,35).

Our preliminary study results , which just finished, looked at effect of 150min/week of aerobic physical activity on EPCs in pre-diabetes population show that interventions even though non pharmaceutical can lead to quick (within 4 weeks) improvement in gene expression and function of CD34+ cells. These cellular changes are reproducible and consistent with other outcome measures such as serum biochemistry and vessel wall dilation measures such as flow mediated dilatation. (34)

Research Hypothesis:

We hypothesize that Linagliptin, a member of DPP-4 inhibitor group of drugs may be able to improve number and function of CD34+ endothelial progenitor cells by up-regulating chemotactic agent SDF1 alpha (DPP-4 degrades SDF-1) and its receptor CXCR4 (7, 20, 21) and thereby improving EPC migration and overall endothelial function. We also propose that this expected cardiovascular benefit is independent of HbA1C reduction. (30, 31)

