2 STUDY OBJECTIVES

2.1 Primary Objective

To investigate the effect of Linagliptin on Endothelial progenitor cells (CD34 positive cells) in patients whose HbA1C is between 6.5 to 10% (both inclusive) while being on treatment with a stable dose of insulin, Metformin, or both for the preceding 3 months before enrollment.

Cellular markers: We will use patient's peripheral blood derived CD34+ cells looking at number, function and gene expression changes pre and post Linagliptin over 12 weeks of therapy.

Urinary Function Marker in CKD: We will estimate 24hr urinary protein estimation and creatinine clearance (This is measured via the micro-albumin/Creatinine ratio provided from a random spot urine sample).

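### The primary outcome is an unranked set of cellular and renal readouts tested at p<0.05 with no control across outcomes, and the one powered readout in that set is never named as primary.

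*Combined protocol and SAP*

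**What the plan says.** **Primary set.** Under Study Outcome Measures, the synopsis puts three cellular domains (number, function, gene expression) and two renal measures under Primary. The cellular entry reads "We will study pre and post Linagliptin treatment changes in number, function and gene expression of" CD34+ cells. Section 2.1 repeats the cellular list, "looking at number, function and gene expression changes pre and post Linagliptin over 12 weeks of therapy", and again adds the renal measures. Neither place ranks them or names a lead variable.

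**Synopsis objective.** It reads "The primary objective is to ascertain if addition of Linagliptin improves CD34+ cell function and gene expression". Number is absent, although the trial title, the synopsis outcome measures and section 2.1 all include it. The renal measures appear there only as something to correlate with the cellular change.

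**Renal measures.** They are primary in the synopsis outcome measures and in section 2.1. They are secondary in the same synopsis list ("Estimation of Creatinine clearance and Proteinuria estimation"), in section 2.2, and under Secondary Measures in the methods text following section 4.5.

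**Testing rule.** The synopsis Statistics entry says "A p-value of less than 0.05 will be considered statistically significant". In section 5, Data Analysis, the one multiplicity provision covers pairwise comparisons of group slopes after a significant interaction test.

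**Power.** Section 5 powers two variables, CD34+/KDR+ cells and VEGF. VEGF is powered in pg/mL, and its ELISA is a Secondary Measure.

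**Status.** The synopsis also says "This is a pilot study as a result appropriate power calculation is not feasible".

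**The concern.** With several unranked primary readouts and one threshold, nobody can say in advance how many primary tests there are or which of them answers the question. The slope adjustment does not help, because it works between groups inside one outcome.

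Two things are at stake. If a single significant domain is later presented as the trial's positive result, the chance of that happening under no effect exceeds 5%. And the stated power belongs to one variable at an undivided alpha, while the synopsis objective does not mention that variable.

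**Working it through.** **1. Which primary readout is powered?** Section 5, Sample Size Estimation, gives for CD34+/KDR+ cells: reference slope 4 per week, SD 15, correlation 0.60 between time points, visits at weeks 0, 6 and 12. A 25% effect is a slope difference of 1 per week, or 12 cells at week 12.

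The visit times have mean 6, so their sum of squares is 36 + 0 + 36 = 72. For a comparison of slopes:

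SE = √[2 × SD² × (1 − ρ) / (n × 72)]

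For n = 18 per group: SE = √[2 × 225 × 0.40 / (18 × 72)] = √(180/1296) = 0.3727, and 1/0.3727 = 2.683.

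**2. Reproduce the stated power.** One-sided alpha 0.05:

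| Effect, n per group | Difference/SE | Computed | Stated |
|---|---|---|---|
| 25%, 18 | 2.683 | Φ(2.683 − 1.645) = 0.850 | 0.84 |
| 25%, 22 | 2.966 | 0.907 | 0.90 |
| 20%, 18 | 2.147 | 0.692 | 0.70 |
| 20%, 20 | 2.263 | 0.732 | 0.73 |

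Two-sided, the first row is Φ(2.683 − 1.960) = 0.765. The plan does not state sidedness, so both versions are carried below. Either way, the power is for one variable with the whole 0.05 spent on it.

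**3. False-positive rate if any one domain suffices.** Take four domains: number, function, gene expression, renal. The two renal measures count once, because section 2.1 takes both from the same spot-urine ratio. Assume one two-sided test per domain at 0.05 and no true effect anywhere.

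- Independent: 1 − 0.95⁴ = 0.185.
- Common correlation r between the normal test statistics: 1 − ∫ φ(z) [Φ((c − z√r)/√(1−r)) − Φ((−c − z√r)/√(1−r))]⁴ dz, with c = 1.960.

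| r | 0.3 | 0.5 | 0.7 | 0.9 |
|---|---|---|---|---|
| Rate | 0.174 | 0.156 | 0.130 | 0.094 |

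The documents give no correlation between readouts, so r is an assumption. The 0.60 in section 5 is between time points of one outcome.

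**4. Cost of splitting alpha instead.** Bonferroni over four domains gives 0.05/4 = 0.0125 each.

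| Setting | One-sided, 0.05 → 0.0125 | Two-sided, 0.05 → 0.0125 |
|---|---|---|
| 25% effect, n = 18 | 0.850 → Φ(2.683 − 2.241) = 0.671 | 0.765 → Φ(2.683 − 2.498) = 0.574 |
| 20% effect, n = 20 | 0.732 → 0.509 | 0.619 → 0.407 |

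**The case against.** **It is a pilot, and says so twice.** In a 40-patient mechanistic study, several readouts without formal error control can be acceptable if they are presented as exploratory. This limits how serious the point is. It does not remove it: the plan still declares significance at 0.05 and states power, and it labels only the optional exosome sub-study exploratory.

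**No success rule is written.** The p<0.05 sentence says when a result is called significant, not when the trial succeeds. A reader might infer that one significant readout is enough, but the documents do not say so. If every domain had to succeed, there would be no inflation. They do not say that either. The percentages are therefore conditional.

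**The cellular lists mostly agree.** This stands. The Introduction's hypothesis that linagliptin "may be able to improve number and function of CD34+ endothelial progenitor cells" might look like a further conflict because gene expression is missing, but a mechanistic hypothesis does not designate an endpoint. The inconsistencies to reconcile are the missing number in the synopsis objective and the double listing of the renal measures.

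**Stronger readings that the documents do not support.**
- A reader might count every FACS tube, gene and assay dose and quote a far higher error rate. The assay list is not an endpoint list. Several FACS tubes carry no CD34 label, and one tube is unlabelled.
- A reader might infer from section 4.4 that early clinical unblinding invites a choice of lead cellular readout. That section also requires all data to be collected and a data lock, and it allows the early step only once the cellular data are acquired and compiled. It adds little to the basic problem.
- A reader might say that the powered variable has no usable unit. Section 5 speaks of cells and the FACS plan of percentages, but each tube holds 1 million cells, so the two can be converted. This is a reporting detail to settle.

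**Conclusion.** The point holds. The primary set is unranked, nothing controls error across its members, the synopsis objective omits the powered domain, and the renal measures have two statuses. CD34+/KDR+ number is the only powered variable in the primary set, and nothing in the plan names it as primary.

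The size is about 19% false positives for four independent domains, and 17% down to 9% at correlations of 0.3 to 0.9, against a nominal 5%. It rests on three assumptions: one test per domain, no true effect, and any single p<0.05 counting as success. It should be corrected. Given the declared pilot status, nothing stronger than that is warranted.

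**What to change.** In a dated amendment, made before any unblinding:

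1. Name one lead primary readout. The natural choice is the linagliptin–placebo group-by-time difference in CD34+/KDR+ cells over weeks 0 to 12, because the stated power applies to it. Which readout leads remains the investigators' decision, but a different choice would need its own power statement.
2. State its unit. Also state which form of the interaction decides, since Data Analysis leaves time either linear or as two indicators.
3. Reword the synopsis primary objective to match.
4. List the renal measures once.
5. Label function, gene-expression and renal readouts secondary or exploratory. Report them as estimates with 95% confidence intervals, with false-discovery-rate control in the gene panel.

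A single primary keeps alpha at 0.05 and the stated power. Splitting alpha over four domains would not: at n = 18 per group and a 25% effect, power falls from about 85% to 67% one-sided (the version that matches the stated 84%), or from 77% to 57% two-sided.

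The cost is wording and analysis only, with no added patients, visits or assays. There are two downsides. Function and gene expression, which the synopsis objective names, lose primary status, and fewer results can be called significant. And version 6.9 is dated June 2017, while the estimated first patient visit was September 2015. If recruitment kept to that estimate, this is a mid-trial endpoint change and should be documented as such.

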5 STATISTICAL CONSIDERATIONS

Statistical Analysis:

Sample Size Estimation:

The total sample size requested, accounting for attrition over the 12-week period, is 20 subjects per group or 40 subjects total. We plan to allow for 25% attrition (drop out), therefore plan to screen 55 patients over three years.

Sample size estimates were based on the effects of exercise on CD34+/KDR+ cells and VEGF, as described in the literature (47-50).

This is a pilot study and accurate power calculation is not feasible.

The effect of a single session, as well as extended training, on healthy subjects or those with existing cardiovascular conditions appears to increase the CD34+/KDR+ cells and VEGF.

To compute sample size we used the approach suggested by Diggle, Liang, & Zeger (1994)(51) which compares the rates of change in the two study groups over time. This approach incorporates the number and interval of time points and the correlation among repeated measures. For this study, we will employ one baseline and two follow-up measures at 6 and 12 weeks. Further, we will assume a correlation 0.60 among repeated measures of the outcome. We consider this a conservative estimate since Frison and Pocock (1992) (52) suggest a correlation of 0.65 as reasonable in the absence of an existing estimate. We also note that as this correlation increases, statistical power also increases.

The results in the table below show the expected mean difference in study groups at the end of follow-up, as well as the average rate of change in the two groups at 80% power and 90% power. To estimate the effect of Linagliptin on the CD34+/KDR+ cells, we expect that the effect would be at least 25% greater than the effect seen for exercise alone. Using the results from Sandri et al. (2005)⁴⁹ for the rate of change and the variability, the CD34+/KDR+ cells increased an average rate of about 4/wk with a standard deviation of about 15. Thus, for a 25% increase in the rate of change for the CD34+/KDR+ cells due to Linagliptin, a sample size of 18 subjects per group would provide about 84% power, assuming measures taken at baseline and 2 equally-spaced time points over 12 weeks. At the conclusion of follow-up, we would expect study groups to differ by an average of 12 cells. If the effect of Linagliptin is only 20%, a sample of 18 would provide about 70% power, whereas a sample of 20 would provide about 73% power.

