For VEGF, the results from Sandri et al. (2005)(49) were mixed with one study group showing a .6 pg/mL per week increase and another showing a 0.5 pg/mL per week decrease after 4 weeks of training. If we assume that Linagliptin will increase VEGF consistently at 0.3 pg/mL per week difference in slopes compared with exercise alone, then assuming a standard deviation of 5 and correlation or 0.60 among repeated measures, a sample size of 18 per group would provide about 77% power to detect a difference in slopes of 0.3 pg/mL per week or a mean difference in the groups at the end of the study of 3.6 pg/mL. A sample size of 27 would provide about 90% power to detect the same effects.

Thus, we feel that a sample size of at least 18 subjects per group with complete data would provide sufficient power for the study outcomes. In order to insure that we will have 18 per group who complete the study, we will enroll 20 subjects per group in order to account for attrition over the 12-week intervention period.

Biochemical Measure	Mean difference at end of 12 weeks	Sample Size per group	Power
CD34+/KDR+	12 cells	18	0.84

cells	(25% increase; 4/wk vs. 5/wk)	22	0.90
VEGF, pg/mL	3.6 pg/mL (50% increase; (0.6/wk vs. 0.9/wk)	18	0.77
		27	0.90

Sub-Group Subject Number Breakdown:

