To estimate the effect of linagliptin on CD34+/KDR+ cells, we originally proposed a sample size of 20 per group in 2 groups, giving us power = .73, assuming alpha=.05, between time points of .60 and equal allocation between groups. Thus, the group x time interaction effect size we were modeling was an interaction that explained 3% of total variance, or a partial eta-square = .0291. Using 3 groups (Insulin only, metformin only, metformin + insulin), with the same effect size, we would achieve this same level of power using a total sample size of 51 (17 per group). However, given the relatively small numbers of potential participants with insulin-only (n=21) and insulin+metformin (n=54), and the relative large number with Metformin only (260), we will need to change the allocation ratio between groups. Maintaining the same total sample size as originally proposed (40), we will allocate patients from each group in the following numbers: **Metformin only (22), Metformin+insulin (12), Insulin only (6)**. We recognize that we will be underpowered for comparisons between the Metformin + insulin versus Insulin groups. However, comparisons with the Metformin-only group will still have reasonable power. Given the small number of potential patients with Insulin-only, this is a feasible strategy for including this group in the analysis.

Data Analysis.

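### The synopsis's 73% power assumes 20 per group with no loss and an unnamed 20% effect, not the 18 completers planned; the 25% and 10% attrition figures also need reconciling

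*Combined protocol and SAP*

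**What the plan says.** The Statistics row of the synopsis gives the requested size, "after accounting for attrition over the 12-week period, is 20 subjects per group", and in its next paragraph reports the power: "We however did conduct power analysis, which provided us with 73% power (see statistics section". It names no effect size, number of completers or sidedness.

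Section 5, Sample Size Estimation, supplies the basis for CD34+/KDR+ cells:

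- For the main assumption, a 25% faster rise than with exercise alone: "a sample size of 18 subjects per group would provide about 84% power".
- For an effect of only 20%: "a sample of 18 would provide about 70% power, whereas a sample of 20 would provide about 73% power".
- On the number needed: "a sample size of at least 18 subjects per group with complete data would provide sufficient power for the study outcomes".
- On enrolment: "In order to insure that we will have 18 per group who complete the study, we will enroll 20 subjects per group".
- On screening: "We plan to allow for 25% attrition (drop out), therefore plan to screen 55 patients over three years".

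The Sub-Group Subject Number Breakdown in the same section repeats the 73%: "we originally proposed a sample size of 20 per group in 2 groups, giving us power = .73, assuming alpha=.05". It does not mention completers or the 20% effect there.

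**The concern.** Two statements do not fit together.

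First, a sample size described as allowing for attrition is followed by a power that allows for none. A reader who stops at the synopsis will probably take 73% as the power once drop-outs are gone. That reader will not learn that it belongs to the smaller of two effects, or that the main assumption gives 84%.

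Second, Section 5 contains two attrition rates. One is stated as 25% and called drop-out. The other is implied as 10% by enrolling 20 to keep 18. If the 25% really were loss after randomisation, enrolling 20 would not deliver the 18 complete cases that the plan calls sufficient, and the powers at 18 would not describe the trial as run.

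**Working it through.** **Inputs, all from Section 5.** Visits at weeks 0, 6 and 12; correlation 0.60; SD 15 and control slope 4 per week for CD34+/KDR+ cells, so slope differences of 1.0 (25%) and 0.8 (20%) per week; for VEGF, SD 5 and slope difference 0.3 per week; alpha 0.05, sidedness not stated.

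**Formula.** The plan names a comparison of rates of change between two groups. With S the sum of squared deviations of the visit times, S = (0−6)² + (6−6)² + (12−6)² = 72. The slope variance per patient is SD²(1−ρ)/S = 225 × 0.4/72 = 1.25 for the cells and 25 × 0.4/72 = 0.139 for VEGF. With n per group, SE = √(2 × variance/n) and power = Φ(d/SE − z).

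**Reproducing the 73%.** At n = 20, SE = √(2.5/20) = 0.354 and 0.8/0.354 = 2.263. One-sided, 2.263 − 1.645 = 0.618, so power is 0.732. Two-sided, 2.263 − 1.960 = 0.303, so power is 0.619.

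| Effect | n per group | Stated | One-sided 0.05 | Two-sided 0.05 |
|---|---|---|---|---|
| 20% | 20 | 0.73 | 0.732 | 0.619 |
| 20% | 18 | 0.70 | 0.692 | 0.574 |
| 25% | 18 | 0.84 | 0.85 | 0.765 |
| 25% | 22 | 0.90 | 0.907 | 0.843 |
| VEGF | 18 | 0.77 | 0.779 | 0.675 |
| VEGF | 27 | 0.90 | 0.905 | 0.841 |

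Every stated power reproduces one-sided and none two-sided. The 73% is the figure for 20 complete cases per group and the 20% effect.

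**At the planned completers.** The expected loss is 1 − 18/20 = 10%. On the plan's own figures, 73 − 70 = 3 points too high for the 20% effect and 84 − 73 = 11 points too low for the 25% effect.

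**Credit for partial data.** The planned mixed model keeps incomplete patients. Assume that both drop-outs per group supply weeks 0 and 6. Those two visits alone have S = 18, so counting within-patient slope information only gives (18 × 72 + 2 × 18)/72 = 18.5 effective patients and one-sided power 0.702. Generalised least squares gives 18.6 and 0.705. Both are still about 70%.

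**The two attrition rates.**

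- Screening to enrolment: 40/0.75 = 53.3, 55 × 0.75 = 41.25, and 1 − 40/55 = 27.3%. This is a near fit to 25%.
- Screening to completion: 1 − 36/55 = 34.5%. This does not fit.
- Enrolment to completion: 20 × 0.75 = 15 per group, not 18. This contradicts the completer target.

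**If the 25% is loss after randomisation (n = 15 per group).** Power is about 79% (25% effect), 62% (20% effect) and 71% (VEGF) one-sided; about 69%, 50% and 60% two-sided. Keeping 18 completers would need 18/0.75 = 24 per group, 48 in total.

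**The case against.** The strongest reply is that nothing has been miscalculated. The 73% recomputes to 73.2%, and Section 5 attaches it consistently to 20 per group, with the 70% for 18 and the 20% effect in the same sentence. The synopsis mentions attrition when describing the sample size, not the power. It refers the reader to the statistics section and warns that this is a pilot for which a proper power calculation is not feasible. All of that stands, and it makes this a matter of labelling rather than of arithmetic. It does not remove the mismatch: following the cross-reference shows that the quoted power is the no-loss figure, beside a sample size said to allow for loss.

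Two stronger readings should be resisted. A reader might infer that the synopsis inflates the power. The documents do not support that: 73% is below the 84% for the main effect at 18 completers. A reader might also infer that the 25% is simply a screening loss with the wrong label. The arithmetic leans that way, and so do the four weeks between screening and randomisation, with eligibility rechecked at week 0. But the text calls it drop-out, close to a sentence about attrition over the 12 weeks, and nowhere describes it as screening loss. Whether the label or the rate is wrong is not shown.

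**Conclusion.** The inconsistency is real and holds on the plan's own figures. The synopsis power belongs to 20 complete cases per group and an effect it does not name, and it matches neither scenario at the 18 completers planned. The 25% and the implied 10% cannot both be loss after randomisation.

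Severity depends on what the 25% means. If it is loss before randomisation, the point is minor: a 3-point and an 11-point discrepancy in reporting, with no effect on the sample size. If it is loss after randomisation, it is larger, because the target of 18 completers fails and the powers fall to those for 15.

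The comparison of 73% with 70% and 84% rests only on stated figures. The recomputed values assume the normal approximation and the inputs listed. That the plan used a one-sided alpha is inferred from what reproduces its figures. The sidedness question is larger than the 3-point gap (70% becomes about 57%, and 84% about 77%), so the corrected synopsis should not carry these powers without it.

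**What to change.** Keep 40 enrolled and make three changes.

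1. **Synopsis, Statistics row.** Replace the bare 73% with the power at the expected number of completers for each named effect: at 18 per group, about 70% for the 20% effect and about 84% for the 25% effect. State whether alpha is one- or two-sided. If two-sided is intended, these become about 57% and 77%.
2. **Section 5, Sub-Group Subject Number Breakdown.** Keep the .73, since the three-group comparison with 51 subjects is built on it, but label it as 20 per group with complete data and a 20% effect.
3. **Section 5, Sample Size Estimation.** Say what the 25% refers to.
   - If it is loss before randomisation, say so and give 10% as the expected 12-week drop-out.
   - If it is loss after randomisation, state 15 expected completers per group, restate the powers for 15 in the text, table and synopsis in place of those for 18, and revise the statement that enrolling 20 secures 18.

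The first two changes and the first branch of the third cost wording only. In the second branch, 40 can stay only if the completer statement is revised; holding to 18 completers would add 8 patients (48 in total).
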